### *Pulmonary aspiration*

Diagnosed by clear clinical history AND radiological evidence.

## **Clavien-Dindo scale grading**

All reported postoperative complications will be graded on severity by using the Clavien-Dindo scale:

Grade I	Any deviation from the normal post-operative course not requiring pharmacological treatment or surgical, endoscopic or radiological intervention. This does not include drugs such as antiemetics, antipyretics, analgesics, diuretics, electrolytes and physiotherapy.
Grade II	Requiring pharmacological treatment with drugs other than those described in Grade I. Includes blood transfusions and parenteral nutrition.
Grade III	Requires surgical, endoscopic or radiological intervention
Grade IIIa	Intervention not under general anaesthesia

Grade IIIb	Intervention under general anaesthesia
Grade IV	Life-threatening complication requiring critical care admission
Grade IVa	Single organ dysfunction (not including dialysis)
Grade IVb	Multi-organ dysfunction
Grade V	Death

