**Appendix 3 – Secondary outcome definitions (alphabetical)**

## 1. Acute Kidney Injury (AKI)

According to the KDIGO consensus definition of AKI:

Stage	Serum Creatinine	Urine output
1	1.5-1.9x baseline OR ≥0.3mg/dL (≥26.5mmol/L) increase	<0.5ml/kg/hr for 6-12 hours
2	2.0-2.9x baseline	<0.5ml/kg/hr for ≥12 hours
3	3.0x baseline OR ≥4.0mg/dL (≥353.6mmol/L) increase OR initiation of renal replacement therapy	<0.3ml/kg/hr for ≥24 hours OR no urine output for ≥12 hours

If urine output is not measured/recorded, incidence of AKI will be solely based on serum creatinine or commencement of renal replacement therapy.

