**5. Major adverse kidney events (MAKE)**

Composite outcome that includes:

- Renal mortality
- Renal replacement therapy of any duration
- ≥30% decline in eGFR from baseline

Measured at a pre-specified time e.g. 30 days after the index operation

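### The severity scale excludes dialysis from grade IVa and places it nowhere else, so new dialysis for isolated kidney failure has no sub-grade in critical care and no clear grade outside it

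*Combined protocol and SAP*

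**What the plan says.** The last part of Appendix 3 (Clavien-Dindo scale grading) states: "All reported postoperative complications will be graded on severity by using the Clavien-Dindo scale". The rows that matter here are:

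- Grade III: "Requires surgical, endoscopic or radiological intervention".
- Grade IV (parent row): "Life-threatening complication requiring critical care admission".
- Grade IVa: "Single organ dysfunction (not including dialysis", with the bracket closing after the last word.
- Grade IVb: "Multi-organ dysfunction".

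Grade II covers drug treatment beyond that allowed in grade I, and also transfusion and parenteral nutrition. Dialysis or renal replacement therapy appears in no row other than IVa.

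Earlier in the same appendix, "initiation of renal replacement therapy" is one of the criteria for AKI stage 3, the highest stage. Where urine output is not available, "incidence of AKI will be solely based on serum creatinine or commencement of renal replacement therapy". The MAKE composite includes "Renal replacement therapy of any duration". Section 5.3.5 repeats that component and sets AKI at day 7 and MAKE at day 30. Both are secondary outcomes in section 3.2.

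**The concern.** A severity scale should give each event one grade, and more organ support should not remove the grade. Here the need for dialysis takes isolated kidney failure out of the only single-organ sub-grade in grade IV, and no other row receives it. Yet the AKI and MAKE definitions in the same appendix treat renal replacement therapy as a marker of serious kidney injury.

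What is at stake is consistent grading. Four centres will apply this table. A rater who meets such a patient has to improvise, and raters at different sites may do so differently. In a cohort of 95, one or two inconsistent grades could visibly change a table of severe complications.

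**Working it through.** The protocol gives no figure to reproduce, and the point does not depend on a rate, an effect size or the sample size. The check is to run four cases through the printed rows. Cases 1, 2 and 4 are taken to be life-threatening, as the parent grade IV row requires.

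| Case | Parent IV | IVa | IVb | Result |
|---|---|---|---|---|
| 1. Kidney failure alone, creatinine 3.0 times baseline, no dialysis, in critical care | yes | yes | no | IVa |
| 2. As case 1, with new dialysis | yes | excluded | no, one organ | IV with no letter |
| 3. Kidney failure alone, new dialysis, outside critical care | no | no | no | no clear grade |
| 4. New dialysis plus failure of a second organ, in critical care | yes | no | yes | IVb |

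**Cases 1 and 2.** Both are AKI stage 3 under Appendix 3. They differ only in that the second patient needs dialysis, and that patient loses the sub-grade. The scale therefore gives less information about the patient who needs more support.

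**Case 3.** Without critical care admission the parent row is not met. Grade III needs a surgical, endoscopic or radiological intervention, and the table does not say whether dialysis, or placing access for it, counts. Grade II is defined by drugs, transfusion and parenteral nutrition. Grade I is defined by what the patient does not need, so a literal rater could even arrive there. The table does not settle the choice.

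**Case 4.** This patient is graded without difficulty.

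**Comparison with the kidney outcomes.** Renal replacement therapy started by day 7 makes the patient an AKI stage 3 case and a MAKE case. Therapy first started after day 7 and by day 30 enters MAKE only. Neither classification uses the Clavien-Dindo grade, so the gap cannot change either count.

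**Where the grade is used.** The scale appears only in Appendix 3 and in its reference. Section 3.2 does not list the grade as an outcome, and section 7.3 names no analysis of it.

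**The case against.** The strongest reply is that little is lost. The parent grade IV row carries no dialysis exclusion, so a critical-care patient can be recorded as grade IV and stays in any count of grade III or above. Multi-organ failure is IVb. Every dialysis event within the outcome windows is captured by AKI, MAKE or both. No analysis of the grade is planned. All of this stands, and it sets the size of the point.

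It also rules out several stronger readings that a reader might infer:

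- That every patient with new isolated dialysis is ungraded or graded too low. In critical care only the letter is missing. The grade itself is in doubt only outside critical care.
- That a summary of grade III or above would lose these patients. For critical-care patients it would not, and the protocol plans no such summary.
- That the trial always counts the event twice. It does so only for therapy started by day 7.
- That one to three of about 15 severe complications are at risk. The 15 would come from 0.157 x 95 = 14.9. The 15.7% in section 1.1 is the rate of major complications in a cited cohort at raised cardiovascular risk, and nothing there ties it to Clavien-Dindo grades. The one to three would come from an assumed dialysis rate of 1% to 3% (95 x 0.01 = 0.95 and 95 x 0.03 = 2.85). The documents give no such rate, and it is not split by critical-care status.

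A second reply is that the bracket refers to long-term dialysis that predates surgery. Renal transplant is among the eligible operations in Table 3, so such patients could enrol. The text does not say this, however, and pre-existing dialysis is not a postoperative complication, so the exclusion would then have almost nothing to do. If that was the intention, the line still needs editing.

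**Conclusion.** The point holds as a minor defect of wording with a real but narrow effect. As printed, new dialysis for isolated kidney failure has no sub-grade in critical care and no clear grade outside it, and this does not fit the AKI and MAKE definitions in the same appendix. Only descriptive severity reporting could be distorted. The primary outcome, the AKI and MAKE counts and the sample size of 95 are unaffected. The number of patients concerned cannot be derived from the documents.

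The conclusion rests on reading the printed rows literally. Two further inferences are not supported. One is that the bracket is a copying error: the cited scale is not reproduced, so the documents cannot settle this. The other is that dialysis was meant to move up to IVb: that row names only dysfunction of more than one organ.

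**What to change.** Before any complication is graded, check the grade IVa line against the scale cited as reference 66. Then correct it in Appendix 3, and in the CRF where the scale is used, so that newly started dialysis for single-organ kidney failure has one defined grade, in or out of critical care, consistent with the AKI and MAKE definitions. If the exclusion was meant for dialysis that predates surgery, say so in the line.

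The cost is a one-line edit and a note to the four sites. No procedure, outcome or sample size changes. If some complications have already been graded, the AKI and MAKE records identify the patients who received renal replacement therapy, and only their grades need a second look.
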